**10/17/2022**

## **Study Protocol and Statistical Analysis Plan**

To reach people who had been in car accidents, an announcement was posted on social media, the research was detailed, and volunteers were asked to give their contact information using Google Forms. The volunteers were interviewed and were thoroughly informed about the study, the inclusion requirements were assessed, and a Google Form information comprising data collecting tools will be delivered to the participants who fulfilled the inclusion criteria.

The subjects will be randomly divided into groups and the EMDR 2.0 Group application and mhGAP will be applied to them online. Participants eligible for the applications were randomized to be 30 subjects (in three group). In both groups, the application will be made for three consecutive days. Those who will be unable to finish their applications at this stage will be ruled out of the study. Participants will be requested to complete out forms including data collection tools 1 week and 1 month after completing the applications. Following appropriate processing, the obtained data will be subjected to statistical analysis.

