### **Statistical Analysis**

SPSS 22 package program will be used to perform statistical analyses on study data. Descriptive data will be presented with frequency and percentage for categorical variables and mean and standard deviation for continuous variables. The Pearson Chi-square test for categorical variables and parametric assumptions for continuous variables will be used to compare the pre-application variables of the two groups, followed by the Student's T-test. The repeated measures analysis of variance will be used to see whether EMDR 2.0 Group Application and mhGAP procedures alone resulted in significant changes in the dependent variables and if there will be a difference in changes between the two groups. In cases where the Mauchly test revealed that the sphericity assumption will be violated, the Greenhouse-Geisser adjustment will be used, and the corrected results will be reported. The effect size will be determined using  $\eta^2$ . A value of  $p < 0.05$  will be considered statistically significant.

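### Eta squared is the only effect size named for the comparison of EMDR 2.0 with mhGAP; no between-group difference with a confidence interval is planned

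*Combined protocol and SAP*

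**What the plan says.** All of the analysis text is in the Statistical Analysis section. A repeated measures analysis of variance is to test change under each procedure and "if there will be a difference in changes between the two groups". Size of effect gets one sentence: "The effect size will be determined using" eta squared. The section does not say whether this is classical or partial, or which term of the model it belongs to. A p-value under 0.05 "will be considered statistically significant". Descriptive output includes "mean and standard deviation for continuous variables", with no statement that it will be laid out by group and visit. No between-group mean difference, contrast at a given visit or confidence interval is mentioned.

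Two points in the opening section (Study Protocol and Statistical Analysis Plan) bear on the size of the problem. Participants are to "complete out forms including data collection tools 1 week and 1 month after completing the applications", so with a baseline there are three time points. The sample size reads "Participants eligible for the applications were randomized to be 30 subjects (in three group"), whereas the Statistical Analysis section will "compare the pre-application variables of the two groups". The total could therefore be 30, or 30 in each of two or three groups.

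**The concern.** The comparative question is which procedure reduces symptoms more, by how much, and whether the advantage lasts to 1 month. Eta squared answers none of these parts directly:

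- It is a ratio of sums of squares, so it is never negative and takes the same value whichever procedure is better.
- For the group-by-time term with three time points and two groups, it condenses two degrees of freedom into one number. An early benefit that fades cannot be told from one that lasts.
- It is a share of variance, although both instruments have defined ranges (0 to 88 for IES-R, 0 to 21 for each DASS-21 subscale).
- Its sample value is positive on average when the true effect is zero, and more so in smaller samples.

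At stake is interpretation. In a small trial, a p-value and a bare eta squared make it easy to take a non-significant result as evidence that the procedures are equivalent, or to take a modest eta squared as a real effect. An interval for the difference shows what the data can and cannot exclude.

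**Working it through.** The plan gives no sample-size calculation, expected effect or standard deviation, so it has no figure of its own to reproduce. The inputs from the documents are the three time points, the two or three groups, and 30 as either the total or the number per group. The correlations and IES-R standard deviations below are assumptions.

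**1. Sign.** One mock data set (two groups of 15, three time points) was analysed twice, with the group labels swapped the second time. The differences in change went from -7.12 and -4.70 points to +7.12 and +4.70. Partial eta squared stayed at 0.083 and classical eta squared at 0.014.

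**2. Mean of partial eta squared when there is no effect.** For g groups, N participants and T = 3 time points, the group-by-time term has df1 = 2(g - 1) and df2 = 2(N - g). The null mean is df1/(df1 + df2) = (g - 1)/(N - 1).

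| Reading of the sample size | df1, df2 | Null mean | Null 95th percentile |
|---|---|---|---|
| 30 in total, two groups | 2, 56 | 2/58 = 0.034 | 0.101 |
| 30 in total, three groups | 4, 54 | 4/58 = 0.069 | 0.159 |
| 30 per group, two groups (60) | 2, 116 | 2/118 = 0.017 | 0.050 |
| 30 per group, three groups (90) | 4, 174 | 4/178 = 0.022 | 0.053 |

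The plan also removes people after randomisation ("Those who will be unable to finish their applications at this stage will be ruled out of the study") and gives no rate. If 20% were lost from 30 in two groups, 24 would remain and the null mean would be 2/46 = 0.043.

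**3. Bias when there is an effect.** This was simulated for a single two-group contrast with 400,000 draws. The population value is d²/(d² + 4).

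| d | Population value | Mean eta squared, 15 per group | Mean eta squared, 30 per group |
|---|---|---|---|
| 0.2 | 0.010 | 0.044 | 0.026 |
| 0.5 | 0.059 | 0.090 | 0.074 |
| 0.8 | 0.138 | 0.165 | 0.151 |

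**4. What a bare value hides.** Take 30 in total in two groups and an observed partial eta squared of 0.10. Then F = (0.10/2)/(0.90/56) = 3.11 on 2 and 56 df, and p = 0.052. The 95% interval from the noncentral F distribution runs from 0 to about 0.24. The plan would report 0.10 and the p-value.

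**5. Precision of a signed difference.** The 95% half-width is in units of the outcome SD, for two equal groups with N in total. The correlation r between baseline and follow-up is assumed to be 0.5.

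- Baseline-adjusted: t(0.975, N - 3) × √((1 - r²) × 4/N).
  - N = 30: 2.052 × √(0.75 × 4/30) = 0.65 SD.
  - N = 60: 2.002 × √(0.75 × 4/60) = 0.45 SD.
- Difference in change, the contrast that matches the planned analysis of variance: t(0.975, N - 2) × √(2(1 - r) × 4/N).
  - N = 30: 2.048 × √(4/30) = 0.75 SD.
  - N = 60: 2.002 × √(4/60) = 0.52 SD.

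For r from 0.3 to 0.7, the same formulas at N = 30 give 0.71 down to 0.54 SD with adjustment and 0.89 down to 0.58 SD for change. If the IES-R SD were 15 to 20 points (assumed), 0.65 SD would be 0.65 × 15 = 9.8 to 0.65 × 20 = 13 points.

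**The case against.** The strongest reply is that eta squared is not the plan's only output. Means and standard deviations are promised for continuous variables, and they usually accompany a repeated measures analysis by group and visit. A reader could then see the direction and subtract to get the raw difference. This stands in part. A reader might infer from the choice of eta squared that the trial report could not show which procedure did better. The documents do not support that, because the descriptive output may show it. What remains is that the plan does not commit to that layout. Separate means would also give no interval for the difference, and visit-by-visit SDs do not give the SD of change without the within-person correlation.

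A second reply is that the bias is secondary. This also stands. Upward bias in eta squared changes neither the F test nor its type I error, and the p-value is reported alongside it. It would be wrong to infer that the significance test is invalid. The bias bears on how much, and the missing sign bears on which.

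A third reply is that the sample size is not settled at about 30. That is correct. The wording allows 60 or 90 in total, where the bias is modest. The missing sign, the merged visits and the missing interval do not depend on the sample size.

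Finally, eta squared is conventional for this model. That is a reason to keep it as a supplement, but not as the only measure.

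**Conclusion.** The point holds as a reporting gap in the plan: the between-group question has no pre-specified signed estimate in scale units, no estimate at each visit and no interval. That follows from the text alone. The size of the upward bias depends on the reading of the sample size, with a null mean between 0.017 and 0.069. It is material if 30 is the total and modest if 30 is the number per group. The half-widths rest on the assumed correlation and on two equal groups, and the figures in IES-R points rest also on the assumed SD. The matter is minor beside anything that would affect the validity of the test, but it is cheap to correct and would make the result easier to interpret.

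**What to change.** For IES-R and each DASS-21 subscale, name as the effect estimate the EMDR 2.0 minus mhGAP difference in scale points at 1 week and at 1 month, each with a 95% confidence interval. Estimate it from a model that adjusts for the baseline score (analysis of covariance or equivalent). This is a different model from the planned analysis of variance, so the plan should state that it governs the between-group conclusion. Otherwise its interval and the analysis of variance p-value could point in different directions with no rule for choosing between them.

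Commit to tabulating means and SDs by group and visit. Keep eta squared as a supplement, labelled as partial and tied to a named model term. State the number of groups and the number per group unambiguously, so that the expected precision can be given.

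The cost is a revision of the analysis text and one small additional model per outcome and visit: four outcomes (IES-R and three DASS-21 subscales) at two visits, so eight estimates. No new data or visits are needed. The reported effect will look less precise than a bare eta squared, because the interval makes the existing uncertainty visible.

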#### **The Depression-Anxiety-Stress Scale-21**

The Depression-Anxiety-Stress Scale-21 (DASS-21) will be used in the study to determine the depression, anxiety, and stress symptoms of the participants. The scale has 21 items (Lovibond and Lovibond, 1995). Each question is evaluated on a four-point Likert-type scoring and it has seven items each for depression, anxiety, and stress. The score that can be obtained from the scale for each subdimension changes between 0 and 21. The Turkish validity and reliability study of the scale were conducted by Saricam (2018).

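### No primary outcome or multiplicity rule is stated in this document: if four scores each get one between-arm test at 0.05, the chance of a false positive is about 9% to 16%, not 5%

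*Combined protocol and SAP*

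**What the plan says.** The Statistical Analysis section plans repeated measures analysis of variance for two purposes. One is to see whether each procedure alone "resulted in significant changes in the dependent variables"; the other is to see "if there will be a difference in changes between the two groups". The second is the group-by-time comparison. The section closes with one rule: a p-value below 0.05 "will be considered statistically significant". It does not list the dependent variables.

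The outcome instruments appear under Data Collection Tools. DASS-21 "will be used in the study to determine the depression, anxiety, and stress symptoms of the participants", and it is scored by subscale: "The score that can be obtained from the scale for each subdimension changes between 0 and 21". No DASS-21 total is described. IES-R has a score running from 0 to 88 and three fields (intrusion, avoidance, hyperarousal), and the section does not say whether the fields are analysed separately. On timing, the opening section states: "Participants will be requested to complete out forms including data collection tools 1 week and 1 month after completing the applications".

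Nothing in the document names a primary outcome, ranks the scores, sets a testing order or adjusts for testing several outcomes.

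**The concern.** A 5% threshold limits the error of one test. When several scores are each compared with that threshold and none is designated in advance, the error for the set is larger and is not controlled. The one correction mentioned, Greenhouse-Geisser, adjusts degrees of freedom within a single analysis when sphericity fails. It does nothing about the number of outcomes.

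At stake is how the main result may be read. Under the text as it stands, whichever of depression, anxiety, stress or event impact falls below 0.05 could be presented as the trial's finding, and a reader would take the 5% error rate at face value.

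**Working it through.** The plan states no familywise error rate, power or effect size, so there is no figure of its own to reproduce beyond the per-test threshold.

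**Inputs**

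- Threshold 0.05 per test, from Statistical Analysis. Sidedness is not stated and is taken as two-sided.
- Four scores: three DASS-21 subscales (0-21 each) and the IES-R total (0-88). This count is inferred from the stated score ranges.
- One group-by-time test per score, covering baseline and both follow-ups. The two visits therefore do not add to the count.
- Correlation r between the four scores: not in the document. Assumed equal for all pairs and varied from 0.5 to 0.9.

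**Step 1, independence.** 1 - 0.95^4 = 1 - 0.8145 = 0.185.

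**Step 2, correlated scores.** For k equally correlated normal test statistics with c = 1.96, the chance of at least one false positive is

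1 - ∫ φ(u) · [Φ((c - √r·u)/√(1-r)) - Φ((-c - √r·u)/√(1-r))]^k du.

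| r | k = 4 | k = 7 |
|---|---|---|
| 0.5 | 15.6% | 23.0% |
| 0.6 | 14.4% | 20.5% |
| 0.7 | 13.0% | 17.8% |
| 0.8 | 11.4% | 14.9% |
| 0.9 | 9.4% | 11.4% |

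**Step 3, check against the planned test.** The group-by-time F test was simulated with no true effect, three time points and 10, 15 or 30 participants per arm (20,000 trials per setting). For four scores it gave 15.4% to 16.3% at r = 0.5, 13.2% to 14.1% at r = 0.7 and 9.6% to 9.8% at r = 0.9. The error of each single test stayed close to 5%. The normal approximation is adequate and arm size hardly matters.

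**Step 4, adding the IES-R fields.** The k = 7 column treats all seven scores as equally correlated. If the IES-R total is instead built as the sum of its three fields, and r is the correlation among the six subscales, simulation gives about 21% to 22% at r = 0.5 and 11% to 12% at r = 0.9. Seven independent tests would give 1 - 0.95^7 = 0.302.

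**Step 5, what a single F test leaves open.** The F test does not say which visit differs. Suppose the arm difference in change from baseline is shown at both 1 week and 1 month with 95% confidence intervals. If correlation over time is equal for all pairs of visits, the two changes share a baseline and correlate 0.5. The Step 2 formula with k = 2 and r = 0.5 then gives 9.1% as the chance that at least one interval excludes zero when there is no effect. Simulation with 15 per arm and a within-person correlation of 0.6 agrees, at about 9%. A remedy that adds an interval must therefore also name the contrast.

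**The case against.** The strongest reply is that the document never says each score is tested at 0.05, never lists the dependent variables, and makes no explicit confirmatory claim. That is correct, and it is why the figures are conditional on one test per score. It does not remove the point: a single threshold, plural outcomes and no correction leave this as the natural reading. If another rule is intended, it has to be written down. If the study is meant to be exploratory, the text should say so rather than set a significance rule alone.

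Three stronger readings are tempting, and the document does not support them.

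- *Three arms compared in pairs.* A reader might infer this from "Participants eligible for the applications were randomized to be 30 subjects (in three group" and expect a much larger error rate. But the same section says "In both groups, the application will be made for three consecutive days", the analysis section refers to two groups, and no pairwise testing across three arms is planned. The wording on the number of groups needs reconciling as a separate matter.
- *No primary outcome exists anywhere.* The document is short, and one may be named elsewhere. The point is limited to this text.
- *Selective reporting has occurred or is intended.* The document shows only that nothing in it prevents this.

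It is also fair to say that the choice of primary outcome belongs to the sponsor. IES-R total is a suggestion.

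**Conclusion.** The concern holds in conditional form. With four scores and one group-by-time test each, the chance of at least one false between-arm result is about 9% to 16% for assumed correlations between the scores of 0.9 to 0.5. It is 18.5% if they are independent. Including the three IES-R fields gives about 11% to 21-23% over the same assumed range. These figures rest on an inferred count of tests and on correlations the document does not supply; within-arm or by-visit testing would add to them. The data are not compromised, but the stated rule does not control the error of the trial's overall conclusion. It should be changed.

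**What to change.** Add one paragraph to Statistical Analysis before outcome data are analysed:

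- **Primary outcome.** Name one. IES-R total is suggested because it is the event-specific scale and recruitment is of people who had car accidents; another justified choice is acceptable. Its already planned group-by-time test becomes the single confirmatory test at 0.05.
- **Estimate.** Report the between-arm difference in change with a 95% confidence interval for one pre-named contrast: either one named visit or the average of 1 week and 1 month. Other visits are descriptive.
- **DASS-21 subscales.** Make them secondary, with estimates and 95% confidence intervals and no confirmatory claim. If claims are wanted, state in advance a Holm family of three (0.0167, 0.025, 0.05), tested only if the primary is significant.
- **IES-R fields and within-arm changes.** Descriptive, and not evidence of a difference between arms.
- **If outcome data have already been analysed.** Report all scores and label any primary as post hoc.

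The effect of the Holm option can be shown. If the primary outcome truly differs but no DASS-21 subscale does, three unadjusted tests give a false DASS-21 claim with probability 12.5%, 10.9% or 8.4% at correlations 0.5, 0.7 and 0.9. With Holm this is at most about 4.4%, 3.9% and 3.0%.

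No extra participants, data or new type of primary test are needed. With estimates only, no DASS-21 claim can be made. With the gated option, DASS-21 claims lose power and are barred altogether if the primary misses 0.05. By normal approximation, a subscale effect with 80% power at 0.05 has a mean test statistic of 1.960 + 0.842 = 2.802. At the first Holm step the critical value is 2.394, so power is Φ(2.802 - 2.394) = Φ(0.408), about 66%. After an independent gate with 80% power it is 0.80 × 0.658, about 53%. These are worst-case figures that assume the other subscales show no effect; a positively correlated gate costs less.

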### **Data Collection Tools**

#### **The Socio-Demographic Data Form**

The socio-demographic data form will be developed by the researchers in line with the literature and study objectives. Participant's demographic data such as age, sex, educational level, and profession will be inquired.

#### **The Depression-Anxiety-Stress Scale-21**

The Depression-Anxiety-Stress Scale-21 (DASS-21) will be used in the study to determine the depression, anxiety, and stress symptoms of the participants. The scale has 21 items (Lovibond and Lovibond, 1995). Each question is evaluated on a four-point Likert-type scoring and it has seven items each for depression, anxiety, and stress. The score that can be obtained from the scale for each subdimension changes between 0 and 21. The Turkish validity and reliability study of the scale were conducted by Saricam (2018).

#### **The Impact of Event Scale**

[figure not shown]
The Impact of Event Scale (IES-R) will be applied to measure the amount of effect of persons from an event in the study. It was developed by Weiss and Marmara in 1997 (Weiss, 2007). It is a self-report five-point Likert-type scale and includes 22 items. It evaluates the level of exposure to events in three different fields as "Intrusion," "Avoidance," and "Hyperarousal." The score that can be obtained from the scale varies between 0 and 88. The Turkish validity and reliability studies of the scale were carried out (Çorapçıoğlu et al., 2006).
